8.2 Adverse Event Reporting

Recipients of allogeneic hematopoietic cell transplantation face significant risks. The risk of treatment related morbidity and mortality following allogeneic transplant is related to the underlying disease, disease status at the time of transplant, prior therapies and other coexisting health problems. Significant risks include:

- Infection. Risks include bone marrow suppression, prolonged hospitalization, invasive procedures, prior
 exposure to micro-organisms and immunosuppressive medications for the prevention and treatment of graft
 versus host disease. Infections may be caused by bacteria, viruses, protozoa or fungus.
- Graft versus host disease. Acute GvHD can range from a mild and treatable problem to a life threatening complication. Chronic GvHD can vary from a mild to an extensive disorder affecting almost any body tissue. Chronic GvHD can negatively affect functional status and quality of life.
- Graft failure. Although rare, graft failure is a fatal complication.
- Infertility in both genders and premature menopause in women at risk.
- Relapse. All patients face a risk of relapse. The risk is highest for those patients with active or resistant disease at the time of transplantation.

Definitions used for Reporting

Adverse Event: Any untoward medical occurrence in a patient or clinical investigation subject administered a pharmaceutical product, medical treatment or procedure and which does not necessarily have to have a causal relationship with this treatment. An adverse event can therefore be any unfavorable and unintended sign (including an abnormal laboratory finding), a symptom, or disease temporally associated with the use of a medicinal product, medical treatment or procedure whether or not considered related to medicinal product or treatment.

Life Threatening Adverse Event: Any adverse event that, in the view of the investigator, places the patient at immediate risk of death from the reaction.

Unexpected Adverse Event: An adverse event, the nature or severity of which is not consistent with the applicable product information (Investigator's Brochure, product insert). For studies that do not involve investigational products or devices, an unexpected adverse event is an adverse event that is not described in the transplant medical literature or consent form.

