Serious Adverse Event (SAE): Any adverse event occurring that results in any of the following outcomes: death, a life threatening adverse event, a persistent or significant disability/incapacity, a congenital anomaly, requires intervention to prevent permanent impairment or damage. Unless the Principal Investigator is using an investigational agent, s/he is not bound by the definition in Title 22 CFR. Stanford IRB definition(s) and requirements apply when applicable, Unanticipated Problems Involving Risks to Participants or Others (UPs) and Unanticipated Adverse Device Effect (UAD)

All grades 3-5 organ-related adverse events not due to the primary malignancy or pre-existing condition will be collected from day 0 through resolution of the SAE. Grade 4 infusion reactions will be reported expeditiously and as a separate listing in the FDA Annual Report.

Distinction between Serious and Severe Adverse Events: The term severe is used to describe the intensity (severity) of a specific event, for example mild, moderate or severe. The event itself however, may be of relatively minor medical significance, for example a severe headache. This is not the same as serious, which is based on the patient/event outcome and is usually associated with events that pose a threat to the patient's life or functioning. Seriousness, not severity, serves as a guide for defining regulatory obligations.

All Adverse events will be graded using the NCI Common Terminology Criteria for Adverse Events (CTCAE) version 4.3 found on the following website:

http://ctep.cancer.gov/reporting/ctc.html

The Principal Investigator (PI) or designee will assess each Adverse Event (AE) to determine whether it is expected or unexpected according to the Informed Consent, Protocol Document, or Investigator's Brochure; and its

relationship to the investigational product.

For the purpose of this study, only AE's found to be directly related to a study-mandated intervention will be captured. The following adverse events, if felt to be related to study treatment, will be captured, but not reported as SAEs:

- Hospitalization, prolongation of hospitalization, or escalation of care due to study-mandated intervention
- Disease Relapse
- Any problems with CliniMACS device during cell separation or inability to achieve CD34+ cell and CD3+ cell target doses
- Any positive culture of HSCT product
- Failure to engraft or graft rejection

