All Serious Adverse Events (SAEs) will be tracked until resolution. SAEs will be collected from the time of stem cell infusion until 30 days post cell infusion. SAEs will be reported to the IRB if they meet the definition of expedited reporting per institutional regulations. All AE's and SAE will be reported at continuing renewal.

Reports (copy of faxed MedWatch) will also be sent to Miltenyi Biotec Incorporated, to the director of Regulatory Affairs and Safety Officer at [contact].

Serious Adverse events will be reported on the MedWatch form 3500a when it meets the definition of expedited FDA reporting. All deaths will be examined to determine if they are related to the use of the CliniMACS device or infusion of manipulated product. If the death is determined to be related, the event leading to the death must be reported within 24 hours of the Investigator's awareness of the event.

The following SAEs require expedited reporting (as soon as possible but within at least 7 calendar days of the investigator learning of the event):

Deaths: All deaths up to 100 days post-transplant. This includes deaths from the common and expected grade 3-4 toxicities noted below. Deaths that occur outside of Stanford will be reported within 5 working days of knowledge of the death. It must be noted that obtaining detailed information on the cause and circumstances of a death occurring at another institution can be difficult. Excludes deaths related to relapse of underlying disease, which will reported in the annual report.

All serious and unexpected toxicities defined as those toxicities not identified in the transplant literature or in the consent form and that are felt to be related to protocol-mandated procedures.

The following will not be reported as SAEs:

- Hospitalizations: Approximately 50% of allogeneic transplant recipients will be readmitted to the hospital. The
 most common indications for readmission of an allogeneic HCT recipient are fever, failure to maintain nutritional
 status and graft versus host disease. Only hospitalizations felt to be related to study mandated interventions
 should be reported as SAE's.

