10.2 Stopping Rules

The study includes stopping rules based on the incidence of graft failure (or graft rejection), and acute GVHD.

Stopping rule for primary graft failure: The first 30 enrolled patients (related and unrelated) will be evaluated for the stopping rule for primary graft failure. The trial is stopped if there are \geq b graft failures out of k resolved patients. Only points where stopping is possible are listed.

k	2	4	5	6	8	9	10	12	13	14	15	16	18	19	20	21	23	24	25	26	27	28	30
b	2	3	3	3	4	4	4	5	5	5	5	5	6	6	6	6	7	7	7	7	7	7	8

The stopping rule for graft failure yields the probability of stopping the trial of 0.05 if the rate of graft failure is 0.1. The probability of stopping the trial is 0.41 if the graft failure rate is 0.2, 0.82 if the graft failure rate is 0.3, and 0.96 if the graft failure rate is 0.4.

These probabilities were calculated based on the binomial distribution. The stopping rule was generated as described by Ivanova et al. (40).

If the study reaches a stopping boundary, the study will be suspended. At this point it may be terminated by the PI or submitted to the safety monitor with a description of the failures to date and a rationale for why the study should be continued. Proper use of the stopping rule table will be ensured by the Study Investigator.

Stopping rule for Grade \geq IV toxicity: If any patient develops grade \geq IV acute GvHD, grade \geq IV infection, or any unexpected grade \geq IV toxicity by 4 weeks post-transplant, the protocol will be halted and the processing reevaluated before proceeding.

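### Section 8.2 applies to expedited reporting the test of unexpectedness that it reserves for studies without an investigational product or device, so some related, non-fatal events can miss that route

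*Combined protocol and SAP*

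**What the plan says.** The definitions in section 8.2 call an adverse event unexpected when it is one "the nature or severity of which is not consistent with the applicable product information", and name the Investigator's Brochure and the product insert as that information. A second test, absence from the transplant literature or the consent form, is introduced with a restriction: "For studies that do not involve investigational products or devices".

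Three later parts of 8.2 use the idea again:

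- The investigator assesses whether each event is "expected or unexpected according to the Informed Consent, Protocol Document, or" the Investigator's Brochure.
- The list for expedited reporting, due within 7 calendar days, includes "All serious and unexpected toxicities defined as those toxicities not identified in the transplant literature or in the consent form", with the added condition "and that are felt to be related to protocol-mandated procedures".
- The list of what will not be reported as an SAE includes common, expected, non-fatal grade 3–4 toxicities described in the transplant literature, the product inserts or the consent form.

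Outside 8.2, the stopping rules (10.2, repeated in the synopsis) say of an unexpected grade IV or higher "toxicity by 4 weeks post-transplant, the protocol will be halted and the processing reevaluated before proceeding". No definition is attached to the word there. The synopsis also has the investigator report unexpected, possibly related grade 3 or 4 reactions, again without a definition.

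**The concern.** The expedited-reporting sentence carries almost the same test that the definitions set aside for studies with no investigational product or device. The objectives, in the synopsis and in section 1.0, describe this study as giving access to an investigational device and reagents. On the protocol's own terms, the product-information test is therefore the one that applies.

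The choice matters because the two tests ask different questions. The literature test asks whether transplant recipients are known to have such an event. The product-information test asks whether the event, at this severity, fits what is known of the product. Severe toxicity is well documented after allogeneic transplantation, so the first test is easily met by an event that the device or the processed graft caused. At stake is how quickly a serious, non-fatal, related event is reported outside the site in a 30-patient study whose primary data monitoring rests with the investigator or a designee. No endpoint, sample size or analysis is affected.

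**Working it through.** No arithmetic applies, and the plan gives no figure on this point. The check sets the uses of expectedness side by side and traces events through them.

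| Place | Judged against | Severity | Relatedness | What it drives |
|---|---|---|---|---|
| 8.2, definition | Product information; literature or consent form only where there is no investigational product or device | Counts, in the product-information test | Not required | Meaning of the term |
| 8.2, investigator's assessment | Consent, protocol or Investigator's Brochure | Not stated | Assessed alongside | Classification of each event |
| 8.2, expedited list | Literature or consent form | Not stated | Required | Report within 7 calendar days |
| 8.2, not reported as SAEs | Literature, product inserts or consent form | Grade 3–4, non-fatal | Not mentioned | Removal from SAE reporting |
| Synopsis, investigator's report | Not stated | Grade 3 or 4 | Possibly related | Investigator's report |
| 10.2 and synopsis, halt | Not stated | Grade IV or higher | Not required | Halt, first 4 weeks |

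**Step 1: which test applies.** The study involves an investigational device, so the definitions point to product information. The expedited list uses the other test. Within 8.2 there are four reference sets for one concept.

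**Step 2: an event on which the rules differ.** Take grade 4 hypotension that is serious, non-fatal, not an infusion reaction and judged related to the processed graft. Assume its severity does not fit the product information.

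- Definition: unexpected.
- Investigator's assessment: depends on which of three documents is consulted.
- Expedited list: not included if the transplant literature describes it, although the relatedness condition is met.
- Exclusion list: hypotension is one of the 33 toxicities named there as examples, so the event may also leave SAE reporting. This is a *may*, because the exclusion is for expected toxicities and the event is unexpected by definition.
- Halt rule, if within 4 weeks: depends on a meaning that 10.2 does not give.

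The example is not remote from the device. Section 8.1 names product contamination and anaphylactic reaction to the murine antibody as risks. These could present as sepsis, fever or hypotension, all of which are among the 33.

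**Step 3: events on which the difference does not matter, or matters less.**

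- Grade 4 infusion reactions are expedited with no expectedness test (8.2).
- Deaths to day 100, other than from relapse, are expedited, including deaths from expected toxicities. All deaths are examined for a link to the device or product, and related ones are reported within 24 hours (8.2).
- Events meeting FDA expedited criteria go on the MedWatch form, and events meeting institutional criteria go to the IRB (8.2).
- Grade IV or higher infection and grade IV acute GvHD by week 4 halt the protocol with no expectedness test (10.2 and synopsis). Grade 4 sepsis is an infection, so for sepsis the definition bears on expedited reporting but not on the halt.
- All AEs and SAEs are reported at continuing renewal. What can be lost is mainly speed.

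What remains is serious, non-fatal, related events that are not grade 4 infusion reactions and do not meet FDA or IRB expedited criteria. For the halt rule, it is toxicity other than infection and acute GvHD.

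**The case against.** The best defence is that the sentence is one route among several. Step 3 above lists the others, and the FDA and IRB routes rest on outside criteria, not on the literature test. Section 8.2 also names unanticipated adverse device effects under the IRB requirements. All of this stands and makes the gap much smaller than the sentence alone suggests. It does not close the gap: 8.2 neither defines those outside criteria nor ties them to its own expedited list, and staff following that list would apply the wrong test for a device study.

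The relatedness condition might seem to protect device-related events. It does not, because an event must meet both conditions, and a related event that is in the literature still fails.

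Two stronger readings are tempting. A reader might infer that expedited reporting and the halt rule are almost blind to device-related toxicity. The documents do not support that: several routes ignore expectedness, and nothing in the plan allows a sensitivity to be calculated. A reader might also infer that grade 4 sepsis from a contaminated graft could escape the halt. It could not, by week 4, because infection is an unconditional trigger.

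A further caution stands. Carrying a device-only definition into the halt rule could do harm. That part of the rule has no relatedness condition, and the risks in 8.1 do not include cytopenias or mucositis. If the Investigator's Brochure resembles 8.1, which is an assumption, ordinary grade 4 conditioning toxicity would count as unexpected. The definition in 8.2 also refers to the applicable product information, which is not limited to the device.

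**Conclusion.** The point holds as a contradiction within section 8.2 with a limited consequence. By the protocol's own definition for a study with a device, an event can be unexpected, serious and related, and still not be expedited under the sentence written for such events; the exclusion list may then remove it from SAE reporting too. Separately, the halt rule depends on a word with no stated definition.

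The textual conflict needs no assumption. Its size cannot be given: the Investigator's Brochure is not among the documents, so how many events would change class is unknown. This is a should-fix matter: it concerns the timeliness of safety reporting, and other routes cover part of the ground.

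**What to change.** In section 8.2:

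1. In the expedited-reporting sentence, replace the literature-and-consent test with the section's own definition for studies with a device: nature or severity judged against the applicable product information. Keep the relatedness condition.
2. Align the investigator's expectedness assessment with that definition, so that each event has one classification.
3. State that the exclusion of common and expected grade 3–4 toxicities does not cover events judged related to the device or processed graft that are unexpected under that definition. Without this, the exclusion list could still remove the events that the first change brings in.

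Separately, 10.2 and the matching synopsis text must be reconciled with 8.2 by stating which meaning of *unexpected* the halt rule uses. No particular halt rule is proposed here.

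The cost is a wording amendment and some additional expedited reports. No analysis or sample size changes.

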9 DATA FORMS AND SUBMISSION SCHEDULE

Primary internal data monitoring will be performed by the Principal Investigator or designee. The PI will review data to assure the validity of data, as well as the safety of the subjects. The PI will also monitor the progress of the trial. The PI is responsible for maintaining the clinical protocol, reporting adverse events, assuring that consent is obtained and documented, reporting of unexpected outcomes, and reporting the status of the trial in the continuing renewal report submitted annually to the IRB and SRC. The PI may designate any or all of these tasks to qualified and trained staff.

Patient enrollment and toxicity/reporting will also be entered by the data-manager, coordinator, or designee into the CIBMTR and on the Program's REDCap database by the research staff.

10 MEASUREMENT

10.1 Primary and Secondary Outcome measures

The primary outcome will be severe (grade III/IV) acute graft-versus-host disease.

Secondary outcomes will be engraftment date (ANC>500 for 3 consecutive days, and >80% donor cells in blood), graft failure and graft rejection, immune recovery, infection, CMV infection and disease, EBV-related PTLD transplant-related toxicity and mortality, transplant-related mortality, grade 3/4 stem cell product infusion-related toxicity, relapse, DFS, OS.

10.2 Stopping Rules

The study includes stopping rules based on the incidence of graft failure (or graft rejection), and acute GVHD.

Stopping rule for primary graft failure: The first 30 enrolled patients (related and unrelated) will be evaluated for the stopping rule for primary graft failure. The trial is stopped if there are \geq b graft failures out of k resolved patients. Only points where stopping is possible are listed.

k	2	4	5	6	8	9	10	12	13	14	15	16	18	19	20	21	23	24	25	26	27	28	30
b	2	3	3	3	4	4	4	5	5	5	5	5	6	6	6	6	7	7	7	7	7	7	8

The stopping rule for graft failure yields the probability of stopping the trial of 0.05 if the rate of graft failure is 0.1. The probability of stopping the trial is 0.41 if the graft failure rate is 0.2, 0.82 if the graft failure rate is 0.3, and 0.96 if the graft failure rate is 0.4.

These probabilities were calculated based on the binomial distribution. The stopping rule was generated as described by Ivanova et al. (40).

If the study reaches a stopping boundary, the study will be suspended. At this point it may be terminated by the PI or submitted to the safety monitor with a description of the failures to date and a rationale for why the study should be continued. Proper use of the stopping rule table will be ensured by the Study Investigator.

Stopping rule for Grade \geq IV toxicity: If any patient develops grade \geq IV acute GvHD, grade \geq IV infection, or any unexpected grade \geq IV toxicity by 4 weeks post-transplant, the protocol will be halted and the processing reevaluated before proceeding.

